1.1.2.3 Pharmacokinetic Outcome Measures

The PK outcome measures were as follows:

- Plasma concentrations at each scheduled PK sample time point.

A population PK model previously developed using nonlinear mixed-effects modeling ([1105289](#)) will be used to derive individual measures of exposure at steady state such as:

- Maximum plasma concentration (C_{max})
- Minimum plasma concentration (C_{min})
- The area under the plasma concentration-time curve (AUC_T).

1.1.2.4 Safety Outcome Measures

The safety outcome measures were as follows:

- Incidence and nature of MRI safety findings: amyloid-related imaging abnormality – oedema/effusion (ARIA-E) and amyloid-related imaging abnormality – microhaemorrhages and hemosiderin deposits (ARIA-H)
- Incidence, nature, and severity of serious adverse events (SAEs)
- Incidence, nature, and severity of adverse events (AEs)
- Incidence of treatment discontinuations due to AEs
- Mean changes in clinical laboratory tests from the OLE baseline over time and incidence of abnormal laboratory values and abnormal laboratory values reported as AEs
- Mean changes in ECG assessments from baseline over time and incidence of abnormal ECG assessments
- Incidence of anti-gantenerumab antibodies
- Physical and neurologic examination abnormalities
- Mean change in vital signs assessment from baseline over time and incidence of abnormal vital signs measurements
- Suicidal ideation, suicidal behavior, and self-injurious behavior without suicidal intent, as determined using the Columbia–Suicide Severity Rating Scale (C-SSRS).

1.2 STUDY DESIGN

Study WN28745 was a Phase III, multicenter, randomized, double-blind, placebo-controlled, parallel-group study to evaluate the safety and efficacy of gantenerumab in patients with mild AD.

All patients who were actively enrolled in Study WN28745 (i.e., not discontinued from study drug) were invited to participate to the OLE once the study protocol was approved in their country. Overall, 230 patients who had enrolled in Study WN28745 continued to the OLE. DB treatment allocation of patients and apolipoprotein E (APOE) ϵ 4 status were revealed, and the up-titration schedules were determined depending on APOE ϵ 4 status (0 ϵ 4 as non-carriers and 1 ϵ 4 or 2 ϵ 4 as carriers) and whether patients were previously on placebo or active gantenerumab. There were four titration schedules as follows:

- Carrier patients previously on 225 mg gantenerumab
- Non-carrier patients previously on 225 mg gantenerumab
- Carrier patients previously on 105 mg gantenerumab or on placebo
- Non-carrier patients previously on 105 mg gantenerumab or placebo.

See [Table 1](#) for titration schedules in detail.

At every dose increase, MRI confirmation of no symptomatic ARIA-E, no ARIA-E with Barkhof Grand Total Score (BGTS) > 1, and no more than eight ARIA-H cumulatively as per Section 5.1.4 in the study protocol was required. Patients who did not meet the criteria for up-titration either remained on the same dose or interrupted the study treatment until satisfactory resolution of MRI finding (see Section 5.1.4 in the study protocol).

Table 1 Up-Titration Schedule for Open-Label Extension

Previous Treatment Assignment (APOE ε4 status)	OLE ^a Day 1	OLE Week 4	OLE Week 8	OLE Week 12	OLE Week 16	OLE Week 20	OLE Week ≥ 24
225 mg Gantenerumab (Carriers)	450	450	900	900	1200	1200	1200
225 mg Gantenerumab (Non-carriers)	600	600	1200	1200	1200	1200	1200
105 mg Gantenerumab or Placebo (Carriers)	225	225	450	450	900	900	1200
105 mg Gantenerumab or Placebo (Non-carriers)	300	300	600	600	1200	1200	1200

APOE = apolipoprotein E; OLE = Open-Label Extension.

Note: All numerical amounts presented above are in milligrams (mg).

^a First open-label gantenerumab dose administered following signature of Part 2 ICF.

Patients received open-label gantenerumab for an initial 2 years treatment and up to an additional 3 years beyond the initial 2 years of OLE (5 years of OLE in total), followed by a safety and limited efficacy assessment 4 weeks after the last dose. Patients in the OLE were given the option to continue receiving open-label gantenerumab treatment until the end of 2020. The first dose of open-label gantenerumab was administered after the patient had signed the OLE informed consent form.

At the end of the study, patients were given the option of enrolling in the open-label rollover study (WN41874), aimed at evaluating the safety and tolerability of long-term administration of doses up to 1200 mg of gantenerumab. Patients who did not enroll in Study WN41874 had one additional follow-up visit at 16 weeks after the final dose for safety and limited efficacy assessments.

1.2.1 Treatment Assignment

Patients enrolled in the OLE were not randomized. Depending on their APOE ε4 status and previous treatment assignment (gantenerumab or placebo) in the DB part, OLE patients were assigned to one of the four up-titration dosing schemes presented in [Table 1](#).

1.2.2 Independent Imaging Review Facility

All MRI scans were read and reported by the central reader, in alignment with the processes from both parts of the study. When the central reader identified a new MRI finding, the study center medical staff and the Sponsor were notified, and in the case of relevant new MRI findings as defined in the MRI Review Committee (MRI-C) Charter, the Sponsor, in turn, notified the MRI-C concurrently. The MRI-C was actively involved in the review and had the remit to make recommendations that might deviate from the protocol guidelines, as deemed necessary. The committee reviewed relevant MRI findings as defined in the MRI-C Charter.

1.2.3 Data Monitoring

During the OLE, ARIA findings were monitored on an ongoing basis by the Sponsor's Internal Monitoring Committee (IMC) and an internal MRI-C (iMRI-C). The independent Data Monitoring Committee (iDMC) reviewed relevant safety findings on a regular basis until the majority of patients had reached the target dose. The last iDMC was held on 10 April 2018. Afterwards, the iMRI-C and the IMC continued to review safety findings on a regular basis.

2. STATISTICAL HYPOTHESES

Not Applicable.

3. SAMPLE SIZE DETERMINATION

All patients who have been randomized and were actively enrolled in the study at the time of the amendment approval in their respective country will be eligible to participate in the OLE. Patients who have been discontinued from the study will not be allowed to enroll in the OLE.

4. ANALYSIS POPULATIONS

All Enrolled Population

All enrolled population includes all patients that were enrolled in the OLE.

Safety Evaluable Population

The safety-evaluable (SE) population includes patients who received of at least one dose of gantenerumab during the OLE. Analysis using this population will be performed by previous randomization, which is the treatment assignment in the DB part, and overall or by actually received up-titration scheme (as needed), and overall.

Safety Population with Post Open-Label Extension Baseline Magnetic Resonance Imaging

The safety population with post-OLE baseline MRI includes patients in the SE population who had at least one post-OLE baseline MRI.

5. STATISTICAL ANALYSES

5.1 GENERAL CONSIDERATION

In the following sections, for all continuous variables for which descriptive statistics are indicated, the following statistics will be reported: the number of observations, the mean, median, standard deviation, and minimum and maximum. The 25th and 75th percentiles (Q1 and Q3) will also be reported for selected tables.

Statistical analyses will primarily focus on safety aspects in the OLE. The efficacy analyses, including clinical/cognitive measures, will be descriptive and strictly exploratory in nature:

- The start of OLE is defined as the date when patients received the first dose of gantenerumab in the OLE.
- The OLE baseline is defined as the last available assessment up to and including the first day of study drug intake in the OLE. Thus, the OLE baseline could be in the DB part.
- The end of the study is defined as the date of the last visit (including the last scheduled follow-up visit according to the study protocol) of the last participant in the study.

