During Part 1, the study consisted of a screening period of up to 8 weeks in length for each eligible patient who signs the informed consent and agrees to participate, followed by a double-blind treatment period of 100 weeks and a 52-week follow-up period. In OLE, the study will consist of open-label treatment until the end of 2020 and a 4- or 16-week follow-up period.

Investigational Medicinal Products

Test Product

In Part 2, open-label gantenerumab will be administered by SC injection to all patients with APOE $\epsilon 4$ status (0 $\epsilon 4$ 'non-carriers' and 1 $\epsilon 4$ /2 $\epsilon 4$ 'carriers') with previous dose assignment defining the titration rate to the target dose of 1200 mg every 4 weeks (q4w). Patients with non-carrier status previously on 225 mg gantenerumab will receive a dose of 600 mg q4w for the first 2 doses, followed by 1200 mg q4w thereafter to the end of the study. Patients with non-carrier status previously on placebo or 105 mg gantenerumab will receive a starting dose of 300 mg q4w for the first 2 doses followed by 600 mg q4w for 2 doses, then 1200 mg q4w thereafter to the end of the study.

Patients with carrier status previously on 225 mg gantenerumab will receive a dose of 450 mg q4w for 2 doses, 900 mg q4w for 2 doses, and 1200 mg q4w thereafter to the end of the study. Patients with carrier status previously on placebo or 105 mg gantenerumab will receive a dose of 225 mg q4w for 2 doses, 450 mg q4w for 2 doses, 900 mg q4w for 2 doses, and 1200 mg q4w thereafter to the end of the study. Central MRI results as detailed in Section 5.1.3 will be required prior to every dose increase.

On study drug administration days that include efficacy assessments, study drug must be administered at the clinical site. Study personnel administering study drug must not be involved with any study procedures.

At select sites, on days when only safety is being assessed, there is an option to have study drug administered and applicable safety assessments conducted at a prearranged location away from the study site by a trained health care provider if consent is obtained.

Non-Investigational Medicinal Products

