2. Non-carrier patients previously on 225 mg gantenerumab
3. Carrier patients previously on 105 mg gantenerumab or on placebo
4. Non-carrier patients previously on 105 mg gantenerumab or placebo

Patients who were on 225 mg gantenerumab will be up-titrated according to their APOE ε 4 status as follows: Carriers will be up-titrated to 450 mg for 2 months, followed by 900 mg for 2 months, and then 1200 mg for the duration of the OLE. Non-carriers will

be up-titrated to 600 mg for 2 months followed by 1200 mg for the duration of the OLE (see Table 2).

Similarly, patients who were on 105 mg gantenerumab or placebo will be up-titrated according to their APOE ε4 status as follows: Carriers will be initially treated with 225 mg for 2 months, then up-titrated every 2 months to 450 mg followed by 900 mg until they reach 1200 mg; non-carriers will initially be treated with 300 mg for 2 months then up-titrated to 600 mg for 2 months followed by 1200 mg for the duration of the OLE (see Table 2).

At every dose increase, MRI confirmation of no symptomatic ARIA-E, no ARIA-E with BGTS > 1, or no more than eight ARIA-H cumulatively as per Section 5.1.4 will be required. Patients who do not meet the criteria for up-titration will either remain on the same dose or may be temporarily discontinued from treatment until satisfactory resolution of MRI finding (see Section 5.1.4).

Table 2 Up-Titration Schedule for Open-Label Extension

Previous Treatment Assignment (APOE ε4 status)	OLE ^a Day 1	OLE Week 4	OLE Week 8	OLE Week 12	OLE Week 16	OLE Week 20	OLE Week ≥ 24
225 mg Gantenerumab (Carriers)	450	450	900	900	1200	1200	1200
225 mg Gantenerumab (Non-carriers)	600	600	1200	1200	1200	1200	1200
105 mg Gantenerumab or Placebo (Carriers)	225	225	450	450	900	900	1200
105 mg Gantenerumab or Placebo (Non-carriers)	300	300	600	600	1200	1200	1200

APOE = apolipoprotein E; ICF = informed consent form; OLE = Open-Label Extension.

Note: All numerical amounts presented above are in milligrams (mg).

^a First open-label gantenerumab dose administered following signature of Part 2 ICF.

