Appendix 1 Schedule of Assessments Part 1 (cont.)

Table 2: Year 2 Assessments

Assessment/ Procedure	Treatment Period												Follow-Up		Additional Follow-Up	Unsch ^a
	Wk 56	Wk 60	Wk 64	Wk 68	Wk 72	Wk 76	Wk 80	Wk 84	Wk 88	Wk 92	Wk 96	Wk 100	Wk 104 or Early Term ^a	Wk 116	Wk 152	
Dose Number	15	16	17	18	19	20	21	22	23	24	25	26				
Physical examination													X	X	X	X
Neurologic examination													X	X	X	X
Vital signs ^b	X	X	X	X	X	X	X	X	X	X	X	X	X	X	X	X ^b
12-Lead ECG ^c													X		X	X
Serum chemistry ^d and hematology ^{e, f}					X								X ^d		X	X
PK plasma sample					X								X	X		X
Anti-drug antibody sample					X								X	X		X
Urinalysis ^g																X
Urine pregnancy test ^h	X	X	X	X	X	X	X	X	X	X	X	X				X
Lumbar puncture ^{i, j} and CSF sampling ^{i, k}													X ^k		X ^k	X
MRI scan ^l													X ^{m, n}		X ^m	X
Adverse events	X	X	X	X	X	X	X	X	X	X	X	X	X	X	X	X
Concomitant meds	X	X	X	X	X	X	X	X	X	X	X	X	X	X	X	X
CDR ^o					X								X		X	X
ADAS-Cog13					X								X	X	X	X
ADCS-ADL ^o		X			X			X				X	X	X	X	X
NPI ^o					X								X		X	X
MMSE		X			X			X				X	X	X	X	X

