2.2 ANALYSIS TIMING

The analysis covered in this SAP will include all data from Part 1 for all patients enrolled in study WN28745.

For patients who did not transition into the OLE this will include all data from all visits up to and including the final follow-up visit (Week 152). For patients who transitioned into the OLE, data from all visits up to and including the Week 104/early termination visit (Follow up 1), or last visit prior to first OLE dose, will be included. No data from the OLE will be used. Time windowing will be used to ensure that data from all Week 104/ early termination visits are summarized at the correct time point.

Due to the early transition of this study to an OLE, many patients will not have reached the primary analysis time point as defined in the protocol (Week 104). Consequently, all

analysis results (descriptive and MMRM) will be summarized for Week 48, Week 72 and Week 104.

An interim analysis was originally planned to occur when 50% of patients had completed 104 weeks of double-blind treatment. Due to stopping recruitment into the study and the protocol amendment leading to OLE transition, no such interim analysis will be performed.

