4.1.5 Safety Follow-Up Population

The safety follow-up population will include all patients who did not enter the OLE who had a vital signs visit date, AE start date or study completion or discontinuation date greater than 28 days after their last intake of study-drug in double-blind. It will also include all patients who entered the OLE whose first dose in the OLE was greater than 28 days after their last dose in double-blind. The time each patient spent in follow-up is also defined by these dates.

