5.7.3 Magnetic Resonance Imaging Safety Findings

The MRI safety findings will be analyzed only on the safety population with post-OLE baseline MRI. The incidence and severity of ARIA-E and ARIA-H will be summarized by APOE ϵ 4 genotype and up-titration and overall at each dose level. Recurrence of ARIA-E will be summarized by previous randomization and overall. Other ARIA-E characteristics will be summarized by previous randomization and APOE ϵ 4 genotype and overall, and by up-titration scheme and overall. Same for other ARIA-H

characteristics as well. ARIA-E with CNS symptoms will be summarized by previous randomization and APOE ε4 genotype and overall.

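### The OLE SAP accepts a baseline MRI of any age and no OLE-entry scan is scheduled, so ARIA-H that arose undetected before the OLE may be tabulated at the first OLE dose level

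*SAP*

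**What the plan says.** OLE SAP 5.1 defines baseline once, for all assessments: "The OLE baseline is defined as the last available assessment up to and including the first day of study drug intake in the OLE". It adds that this may fall in the double-blind part. OLE SAP 5.7.3 then reports the incidence and severity of ARIA-E and ARIA-H by APOE ε4 "genotype and up-titration and overall at each dose level", in patients with at least one MRI after OLE baseline. It gives no rule for a finding first seen on the first OLE scan.

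In Protocol Appendix 2, Tables 1–4, the Pre-OLE and OLE Day 1 cells of the MRI row are empty. The first scan belongs to OLE Week 4 and is done 10–20 days after that dose. The footnotes to the same tables call for repeat laboratory tests and efficacy scales if these are more than 6 months old, and a new PET scan if the last is more than 9 months old. MRI has no such footnote.

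In Part 1 (Protocol Appendix 1), MRI is scheduled at screening, Weeks 24, 36 and 48, and then not until the column headed "Wk 104 or Early Term".

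Two sets of provisions could supply a recent scan.

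- **Exit visit.** For patients moving to the OLE, Part 1 SAP 2.2 uses data "up to and including the Week 104/early termination visit (Follow up 1), or last visit prior to first OLE dose".
- **Dose-increase rule.** The protocol synopsis says that central MRI results "will be required prior to every dose increase". Protocol 1.4.7.2 has "At every dose increase, MRI confirmation of no symptomatic ARIA-E" among its conditions, and OLE SAP 1.2 repeats the rule: "no more than eight ARIA-H cumulatively as per Section 5.1.4 in the study protocol was required".

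**The concern.** ARIA by dose level is a main safety output of the OLE. Protocol 1.4.7.2 says the titration schemes also serve to examine a range of starting doses in former placebo patients. The OLE Week 4 scan is the only scheduled scan that informs the first dose step, because the third dose is already at the next level.

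If the comparison scan is old, a new microbleed on the Week 4 scan may date from Part 1, including time on placebo. Tabulated at the first dose level, it would make the starting dose look worse than it is. The OLE SAP does list ARIA-E during the double-blind period and cumulative ARIA-H at OLE baseline (5.3), and double-blind adverse events unresolved at OLE entry (5.7.2). All of these describe findings already detected. Cumulative ARIA-H at baseline comes from the same possibly old scan, so it cannot reveal the problem.

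**Working it through.** The plan gives no figure on this point to reproduce. The check is on dates and schedules.

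**1. When could patients enter?** The last patient was randomized on 9 December 2015 (Part 1 SAP 1). OLE enrolment ran from 3 March 2016 to 31 July 2017 (OLE SAP 1). For that last patient the window is 85/7 = 12.1 to 600/7 = 85.7 weeks after randomization. More generally, 31 July 2017 minus 728 days is 3 August 2015, so anyone randomized after that date who entered did so before Week 104.

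**2. How old could the last scheduled scan be?** Part 1 on-treatment scans are done up to 20 days (2.86 weeks) after the dose. Gap = entry week − (scan week + 0 to 2.86). The screening scan falls 1–8 weeks before Day 1. With no exit, unscheduled or clearance scan:

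| Entry at Part 1 week | Last scheduled scan | Gap (weeks) |
|---|---|---|
| 12 | screening | 13–20 |
| 24 | screening | 25–32 |
| 28, 40, 52 | Week 24, 36, 48 | 1.1–4.0 |
| 36, 48, 60 | Week 24, 36, 48 | 9.1–12.0 |
| 64 | Week 48 | 13.1–16.0 |
| 84 | Week 48 | 33.1–36.0 |
| 100 | Week 48 | 49.1–52.0 |

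**3. What does the first OLE scan look back on?** It falls 28 + 10 to 28 + 20 = 38–48 days (5.4–6.9 weeks) after OLE Day 1. Pre-OLE share of look-back time = gap / (gap + 5.4 to 6.9):

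- entry at Week 12: 13/19.9 to 20/25.4 = 65–79%
- entry at Week 64: 13.1/20.0 to 16.0/21.4 = 66–75%
- entry at Week 100: 49.1/56.0 to 52.0/57.4 = 88–91%

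These are shares of time, not of events.

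**4. Per-patient scale, for illustration only.** Assume the WN25203 ARIA-H incidences in Protocol 1.3.3 (10.9% placebo, 19.2% on 105 mg, 13.1% on 225 mg) cover 104 weeks and accrue evenly. Risk over g weeks = 1 − (1 − p)^(g/104):

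| Gap | Placebo | 105 mg | 225 mg |
|---|---|---|---|
| 12 weeks | 1.3% | 2.4% | 1.6% |
| 26 weeks | 2.8% | 5.2% | 3.4% |
| 52 weeks | 5.6% | 10.1% | 6.8% |

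WN25203 enrolled a prodromal population, and Protocol 1.3.3 calls ARIA time-dependent, so even accrual is a simplification. These risks cannot be turned into patient counts, because the share of the 230 entrants with an old scan is not stated.

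**5. Why mainly ARIA-H?** ARIA-H is counted cumulatively, whereas ARIA-E resolves. At the WN25203 rate for months 9–12 on 225 mg (0.5% per quarter), a year gives 1 − 0.995⁴ = 2.0%.

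**6. Does 5.7.3 count from OLE baseline?** It does not define incident ARIA. Its population is built on having an MRI after OLE baseline, which makes that reading natural, but it remains an inference.

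**The case against.** The strongest reply is that the documents largely provide for a recent scan. On plain wording, going from 225 mg to 450 or 600 mg, or from 105 mg to 225 or 300 mg, is a dose increase, and the synopsis, Protocol 1.4.7.2 and OLE SAP 1.2 all tie MRI clearance to dose increases. Part 1 SAP 2.2 also names the Week 104/early-termination visit first for patients moving to the OLE, and that visit includes an MRI.

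Much of this stands. It probably covers former 225 mg patients, whose first OLE step Protocol 1.4.7.2 calls up-titration. It is less clear for former 105 mg patients, whom the protocol treats as having a starting dose, and least clear for former placebo patients. Protocol 5.1.4.2 ties the scan to the end of a dose level, and Appendix 2 lists no entry scan. The exit visit was not assured either. Part 1 SAP 2.2 allows the last visit before the first OLE dose instead. Protocol 3.1.1 describes the early-termination visit for patients who discontinued study drug, whereas OLE entrants had to be still active. An exit scan could also be old at entry, since Part 1 SAP 4.1.5 provides for "patients who entered the OLE whose first dose in the OLE was greater than 28 days after their last dose in double-blind".

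Three further points are fair.

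- The OLE SAP leaves dataset and output details to other documents, and its baseline list is not exhaustive. A scan-age summary or an attribution rule may exist elsewhere.
- The OLE is non-randomized and descriptive, so no error rate or power is affected. Titration and stopping rules use cumulative ARIA-H and do not depend on this tabulation.
- Deleting Week 4 findings in patients with old scans would force their first-step incidence to zero, which is not a useful sensitivity analysis.

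A reader might infer that patients were escalated without safety imaging. The documents do not support that: clearance scans before increases are required throughout titration, and an empty schedule cell does not show that no entry scan was done.

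**Conclusion.** The point holds as a minor gap in analysis and reporting. OLE SAP 5.1 sets no limit on the age of the baseline MRI, no entry scan is scheduled, and 5.7.3 tabulates ARIA by dose level. Following the plan can therefore credit ARIA-H that arose undetected before OLE Day 1 to the first OLE dose level. The recency rules for laboratory tests, scales and PET show that old assessments at entry were foreseen.

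The conclusion rests on two conditions: that 5.7.3 counts from OLE baseline, and that some entrants had no recent exit, unscheduled or clearance scan. The worst case for a patient still in the treatment period is a scan about 52 weeks old.

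A reader might also infer that the reported ARIA-H incidence is inflated by a known or material number of patients. The documents do not support that. They do not say how many entrants had an old baseline scan, and the number may be near zero. As planned, the reader of the listed outputs cannot tell.

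**What to change.** In OLE SAP 5.7.3:

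1. Summarize the interval from the last pre-OLE MRI to OLE Day 1 (median, range, number over 12 weeks) by previous randomization and by up-titration scheme.
2. If any interval exceeds 12 weeks, keep the planned incidence as the main figure. Add a sensitivity table of first-dose-level and overall ARIA-H and ARIA-E incidence, restricted in both numerator and denominator to patients whose baseline MRI was within 12 weeks of OLE Day 1. If none exceeds 12 weeks, step 1 is enough.
3. Do not remove Week 4 findings while keeping those patients in the denominator, unless that figure is shown only as an explicit lower bound beside the planned one.

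Twelve weeks is the spacing of the Part 1 scans at Weeks 24, 36 and 48. It is a judgement: at a gap of about 7 weeks, pre-OLE time already makes up half of the look-back.

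The cost is one derived variable and one table from data already held, with no added scans or visits. No protocol change is proposed, because OLE enrolment closed on 31 July 2017. The downside is a second, smaller-sample figure to explain. Its patients are also selected: those with ARIA in Part 1 had extra scans (Protocol 5.1.4.1) and are more likely to have a recent baseline.
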